BUFFERED VS. UNBUFFERED LOCAL ANESTHESIA IN MANDIBULAR MOLARS
DIAGNOSED WITH SYMPTOMATIC IRREVERSIBLE PULPITIS: A CONTROLLED,
RANDOMIZED, DOUBLE-BLIND STUDY

NCT05227300

06/30/2022

PRIMARY MATERIALS

2% lidocaine with 1:100,000 epinephrine (Septodont Inc, New Castle, DE) was the only local anesthetic used in our study. A standard dental cartridge of 2% lidocaine w/ 1:100,000 epinephrine contains 1.8mL of solution, and the adult maximum recommended dose equates to 500mg (3.3mg/lb or 13.8 cartridges). For reasons of this study, we used a maximum of 3 total cartridges (5.4mL or 108mg) of 2% lidocaine w/ 1:100,000 epinephrine as the standard anesthetic dosage. The Onset 8.4% Sodium Bicarbonate buffering system is marketed by FDA-approved Onpharma (Carson City, NV) that recommends its concurrent use with 2% lidocaine w/ 1:100k epi. Aside from the sodium bicarbonate buffer itself, Onpharma offers the Onset Mixing Pen along with an Onset Cartridge Connector to properly formulate the buffered local anesthetic solution. The Onpharma Onset mixing protocol was incorporated to properly prepare the buffered 2% lidocaine w/ 1:100,000 epinephrine cartridges. Vitality Scanner 2006 (Vitality Scanner 2006; SybronEndo, Orange, CA) is marketed and sold by Kerr Dental, and was used to confirm pulpal anesthesia via Electric Pulp Testing (EPT). Endo-Ice (1,1,1,2 tetrafluoroethane; Hygenic Corp, Akron, OH) was used to initially confirm vitality and a diagnosis of symptomatic irreversible pulpitis.

VERIFICATION OF BUFFERING CAPACITY

To verify the advertised buffering capacity of an Onset Sodium Bicarbonate Cartridge, a pilot study using 2% lidocaine w/ 1:100k epi with and without an added buffer was completed. Both pH strips (Lab Rat Supplies, <https://www.labrat-supplies.com>) and a calibrated digital pH meter (Dr. meter, <https://drmeter.com>) were used to measure the pH of 2% lidocaine with 1:100k

epinephrine initially. Following Onpharma's Onset directions for use, 0.18mL of sodium bicarbonate buffer was added to a 1.8mL cartridge of 2% lidocaine with 1:100k epinephrine. This quantity of added buffer is commonly suggested by the manufacturer, and a historically recommended 10% ratio of sodium bicarbonate buffer to local anesthetic. The respective pH of each anesthetic group was recorded using each company's directions for use. Using the pH strips, we were able to observe that the 8.4% sodium bicarbonate buffer produced a pH between 8 and 9, while the calibrated digital pH meter indicated a reading of 8.08. Using the pH strips, standard 2% lidocaine w/ 1:100k epi had a pH between 4 and 5, and 2% lidocaine w/ 1:100k epi plus 0.18mL of added buffer had a pH between 7 and 8. The digital pH meter produced a reading of 4.35 for standard 2% lidocaine w/ 1:100k epi [94], and a pH of 7.34 for 2% lidocaine w/ 1:100k epi plus 0.18mL of added buffer (no precipitate ever formed). Ultimately, we were able to independently verify that the buffering capacity of Onpharma's Onset sodium bicarbonate buffer system is as advertised using 2 different method.

INCLUSION CRITERIA

To participate, subjects must be between the ages of 18 and 80 years old, have the ability and willingness to independently consent to treatment and study participation. They must have an uncomplicated medical history (ASA I and II), not be pregnant, and have no allergies to local anesthetics/sulfites (confirmed or self-reported). Due to concerns about plasma half-life concentrations, they must not be taking any medications that may affect the proper assessment of the anesthetic (no acetaminophen or short-acting NSAIDs such as ibuprofen within the previous 6 hours [96] [97]; no long-acting NSAIDs such as naproxen within the previous 16 hours). They must not require nitrous oxide during treatment, and the injection area should appear healthy

with no other pre-existing conditions or infections that may compromise an accurate collection of data. Since a localized periodontal examination is a routine portion of the endodontic examination, the potential presence of periodontal disease will not interfere in making a proper endodontic diagnosis. Subjects also must be experiencing signs of irreversible pulpitis (an exaggerated response to cold that lingers longer than 10 seconds) in a mandibular molar at the time of conducting the study.

EXCLUSION CRITERIA

No subjects will have a negative response to cold in the proposed treatment tooth. Also, no subject may have a radiographic periradicular pathosis more advanced than a widened periodontal ligament or have an intraoral swelling.

RECRUITMENT AND ENROLLMENT OF EXPERIMENTAL SUBJECTS

Potential research subjects were pooled from patients scheduled to receive an endodontic evaluation and/or a non-surgical root canal therapy (NSRCT) in the Graduate Endodontic clinic at Indiana University School of Dentistry. All 7 endodontic residents were eligible to screen, diagnose, explain the study goals, and consent patients presenting to the graduate clinic with symptomatic irreversible pulpitis of a mandibular molar. It is important to note that a general script was provided to each endodontic resident outlining key points to discuss with prospective study participants to establish some uniformity in the consenting process and calibration of residents. Each prospective study participant was explicitly made aware that using 2% lidocaine

w/ 1:100k epi is a standard anesthetic option in endodontic treatment regardless of their participation in the research study and the addition of a sodium bicarbonate buffer would not lead to a decrease in its efficacy. Participants were further informed that the addition of the buffer would either have no effect or actually improve the efficacy of a standard, customary local anesthetic.

If an endodontic resident other than the student researcher made a relevant diagnosis, all inclusion/exclusion criteria were respected, and the patient consented to both an NSRCT and participating in the study, then the student researcher was notified. Once the student researcher confirmed all pre-requisites and answered any questions, a trained research assistant prepared a maximum of 3 cartridges of the respective local anesthetic formulation as determined by the randomization scheme immediately prior to the planned administration. A professional statistician helped provide a two-product randomization scheme that randomized each of the potential 60 subjects on the order of their entry into the study. Only the blinded student researcher was eligible to administer the local anesthetic. However, all endodontic residents were calibrated and eligible to acquire and record the data (soft tissue anesthesia as later described, EPT readings, and any pertinent patient discomfort experienced upon access/pulpotomy as reflected on the Wong-Baker FACES Visual Analog Scale) obtained after the student researcher finished giving all 3 cartridges of anesthetic.

DIAGNOSIS

The patient's current chief complaint was recorded; "It hurts when I drink cold...", etc. The tooth/teeth that the patient complained about and the control teeth were subject to standard pulp sensibility testing to ensure a proper diagnosis of symptomatic irreversible pulpitis. If

applicable, this diagnosis was specifically confirmed on the same day that the warranted endodontic treatment was rendered. Prospective study participants were given brief instructions on cold and EPT usage/expectations. Regarding the cold testing, a cotton pellet was held with cotton forceps and thoroughly sprayed with Endo-Ice (Coltene) at -26.2 Celsius until the cotton pellet was soaked. The cotton pellet was then applied to the mid-buccal, natural surface of the tooth, and the patient's response was monitored. The soaked cotton pellet was removed once the patient felt a painful sensation on the tested tooth or if no sensation was felt after 10 seconds of an application. If pain was felt, the amount of time until the sensation subsided was measured. A continued pain for 10 seconds or longer was considered "lingering" pain. Exaggerated or lingering pain, as compared to adjacent or control teeth, was considered acute pain and further quantified on the Wong-Baker FACES Visual Analog Scale (VAS), ranging from 0-10. Patients were immediately presented with this VAS, and their baseline response was recorded. After any previously induced pain had subsided, an electrical pulp testing exam was done using an Electric Pulp Tester (EPT) Sybron Analytic to establish a baseline reading. A 2-3 mm dab of toothpaste was placed on the dried buccal tooth structure. The tip of the EPT was placed on the toothpaste and the EPT was activated once the patient held the end of the wand, thereby completing the circuit. The test was stopped when the patient felt pain or a "tingling" sensation after letting go of the wand or if the measurements reached a maximum value of 80. The EPT number was recorded by the resident on a designated data sheet. Ultimately, a diagnosis of symptomatic irreversible pulpitis was made if the patient had acute, lingering pain cold as compared to the control tooth.

BUFFERED ANESTHETIC PREPARATION

Although other local anesthetics may still be employed, Onpharma markets its Onset sodium bicarbonate buffer to ideally be used in combination with a standard cartridge of 2% lidocaine w/ 1:100k epi. Each of the Onset Sodium Bicarbonate Inj., 8.4%, USP Neutralizing Additive Solution cartridges contain 1.7 mL volume and are packaged in a four-cartridge package. A single cartridge can buffer 10 injections, 40 injections per 4-pack. Onset Sodium Bicarbonate Cartridges have a 3-year shelf life, but once a cartridge is placed in the Mixing Pen, the cartridge should ideally be used within 7 days. Before using, the Onset Mixing Pen was disassembled into its 2 parts, and a 3mL size cartridge was inserted into the Cartridge Chamber. The Mixing Pen should be re-assembled, and a 2nd fluid container (the 1.8mL anesthetic cartridge) was attached to the end of the Pen. To assist the attachment of the anesthetic cartridge to the end of the Pen, an Onset Cartridge Connector was used. Each number on the Mixing Pen corresponds with approximately .01 mL's of fluid, so the Pen's volume dispensing dial was adjusted to setting "18." Ultimately 0.18mL of 8.4% sodium bicarbonate was transferred from the 3mL size cartridge into the lidocaine cartridge after the equivalent amount of anesthetic was displaced into the holding reservoir, resulting in a 10% buffered local anesthetic. This process was repeated by a trained research assistant to produce 3 equivalently buffered cartridges of 2% lidocaine with 1:100,000 epinephrine immediately before it was given to the blinded student researcher.

QUALITY ASSURANCE

The same calibrated electronic pH meter (Dr.meter PH838) that was employed to test the pH in the pilot study was used to test a Sodium Bicarbonate Cartridge from the experimental pack and a cartridge of the standard 2% lidocaine w/ 1:100k epi from an experimental anesthetic package prior to the first administration of the study. Using the pH strips, standard 2% lidocaine

w/ 1:100k epi had a pH between 4 and 5, and 2% lidocaine w/ 1:100k epi plus 0.18mL of added buffer had a pH between 7 and 8. The digital pH meter produced a reading of 4.99 for standard 2% lidocaine w/ 1:100k epi, and a pH of 7.14 for 2% lidocaine w/ 1:100k epi plus 0.18mL of added buffer (no precipitate ever formed). These quality assurance measures are reflected in Figures 11-14. Ultimately, we were again able to independently verify that the buffering capacity of Onpharma's Onset sodium bicarbonate buffer system is as advertised using 2 different methods [94, 95] prior to using those packages of local anesthetic and Onset buffer on our first research participant.

ANESTHETIC ADMINISTRATION

After applying topical benzocaine to the respective administration sites for 1 minute, the student researcher administered 2 cartridges (3.6mL) of the previously determined formulation of 2% lidocaine w/ 1:100,000 epinephrine via IANB at the rate of 1.8mL per minute. Any patients who did not have signs of soft tissue anesthesia (successful IANB) within the following 10 minutes would receive a supplementary 1/2 cartridge (0.9mL) of the same anesthetic formulation via buccal infiltration and a 1/2 cartridge (0.9mL) via lingual infiltration at the affected tooth's apex with a rate of 1.8mL per minute. Along with being a commonplace clinical practice, previous studies have demonstrated an added effectiveness of supplementary buccal and lingual infiltrations in obtaining pulpal anesthesia.

ANESTHETIC TESTING AND DOCUMENTATION

Using an online stopwatch, the student researcher started the timer after administering both IANBs and then continually assessed soft tissue anesthesia of the respective side of the

mandible. Soft tissue anesthesia was considered profound when the patient subjectively attested that their lip, chin, and tongue on the respective treatment side felt “full” or “numb,” and a light stimulation with the tip of an explorer did not elicit any sensation other than pressure as compared to a “sharp” feeling the contralateral side. In the event that the patient denied any signs of soft tissue anesthesia (absolutely no change in feeling) 10 minutes after the 2 cartridges of anesthetic were given via inferior alveolar nerve block (IANB), then the blocks were to be considered “missed,” and the patient would need to be re-blocked as clinically appropriate. This situation would be grounds for withdrawing the patient from the study (with documentation) since a lack of anesthesia following the protocol cannot be attributed to the anesthetic formulation itself but rather operator technique/variable patient anatomy.

Once the patient attested to having soft tissue anesthesia, the amount of time surpassed since being blocked was documented on the designated datasheet, and the supplemental buccal and lingual infiltrations were then administered as previously described. The student researcher or other residents waited 2 minutes after all 3 cartridges of local anesthesia had been administered and then obtained an updated EPT reading on the tooth being treated. An EPT=80 (maximum stimulation) indicated profound pulpal anesthesia, and the endodontic access was initiated. An EPT \neq 80 indicated a need to wait an additional time. We retested the tooth being treated using EPT at 2-minute intervals until EPT=80 or when a maximum of 20 minutes had passed since administering 2 IANBs. According to Whitcomb et al., waiting 10-15 minutes after administering the IANB should be adequate time to allow the onset of pulpal anesthesia in molars. Once EPT=80, the reading was reconfirmed in order to get a consecutive EPT=80 a minute after the initial reading. Participants who did not demonstrate *total* soft tissue and/or pulpal anesthesia within 20 minutes would be categorized as a failure and further managed

according to the best clinical practice (additional block/supplementary injections) so that the endodontic treatment could continue appropriately. After confirming soft tissue anesthesia and 2 consecutive EPT=80, the endodontic treatment could begin.

Upon the completion of the pulpotomy, the patient was shown the same Visual Analog Scale to re-assess their level of comfort. However, any discomfort recognized during the pulpal access or pulpotomy paused the procedure, and the VAS was shown immediately. Patients who indicated moderate or severe pain (VAS scores of 4 or higher) elicited from the tooth undergoing treatment upon pulpal access or a complete pulpotomy were categorized as an anesthesia failure (lack of profoundness) and appropriately managed as previously described. Patients who indicated no pain or mild pain (VAS scores of 3 or lower) were categorized as an anesthesia success (obtained profoundness), and the endodontic treatment continued. When co-residents rendered the clinical endodontic treatment, they recorded and reported these failures to the student researcher after appropriately treating their patient. The student researcher charted the data for each uniquely identified study participant regarding the initial EPT readings (treated tooth and control), the amount of time taken to reach both soft tissue and pulpal anesthesia, VAS scores after both cold testing (baseline) and pulpotomy, and any other conditions that may have led to a “failed” profoundness of anesthesia.

STUDY PROCEDURES

1. Reviewed medical history as a standard of care for endodontic treatment (about 3-5 minutes)
2. Standard of care dental exam with sensibility testing that established baseline EPT reading and VAS score (about 5-10 minutes)

3. Reviewed inclusion/exclusion criteria using data collected in steps 1 and 2 for a standard of care to ensure that the subject qualified to continue with the study (about 3 minutes)
4. Performed consenting procedures for both the Non-surgical Root Canal Therapy (NSRCT) and the research study (about 5-10 minutes)
5. A trained research assistant prepared the cartridges of the type of anesthetic formulation (buffered vs. unbuffered) determined by the randomization scheme in a separate room immediately prior to it being administered. The assistant made a record using a unique identifying code for the type given to each patient. The Onpharma Onset protocol was used when indicated. The assistant “prepared” the unbuffered cartridges in the same amount of time as required for the buffered cartridges, as well as “puncturing” the unbuffered cartridges with the Onset pen so that each cartridge had a uniform appearance (about 3 minutes)
6. Applied 20% topical benzocaine jelly (Ultradent Products Inc, South Jordan, UT) after thoroughly drying the tissues surrounding the inferior alveolar nerve block (IANB) injection site, buccal vestibule, and lingual vestibule of the treatment tooth (about 1 minute)
7. The student researcher administered the 2 IANBs (about 2 minutes) and then started the timer immediately
8. The patient was regularly re-assessed for soft tissue anesthesia (as previously described)
 - a. If within 10 minutes the patient had confirmed soft tissue anesthesia, then the IANBs were considered successful, and 1 cartridge of the respective

anesthetic formulation was supplementarily administered via apical buccal and lingual infiltrations (documented exact time elapsed)

- b. If at 10 minutes the patient did not have any indications of soft tissue anesthesia, then IANBs would be considered missed, and the patient would be withdrawn from the study. Administer additional local anesthetic as clinically appropriate

9. Tested the treatment tooth using EPT in 2-minute intervals (starting at 2 minutes post-supplementary infiltrations)
 - a. If within 20 minutes post-IANBs pulpal anesthesia was confirmed with 2 consecutive EPT=80, initiated NSRCT (document exact time elapsed)
 - b. If at 20 minutes post-IANBs pulpal anesthesia was not confirmed with 2 consecutive EPT=80, anesthesia was considered a failure, and additional local anesthetic was administered as clinically appropriate
10. All pertinent data, including the patient's VAS comfort assessment after pulp chamber access/pulpotomy, were recorded and analyzed with the help a professional statistician for statistical significance.

STATISTICAL ANALYSIS

The buffered anesthetic and unbuffered anesthetic groups were compared for differences in the percentage of subjects who achieved profound pulpal anesthesia using chi-square tests. The time needed to achieve profound pulpal anesthesia using buffered anesthetics and unbuffered anesthetics was compared using Kaplan-Meier survival curves and log-rank tests. A 5% significance level was used for all tests. Comparisons of the VAS results were made using a

Wilcoxon Rank Sum test. Up to 60 subjects were randomized to ensure that 40 evaluable subjects could complete the study. With a sample size of 20 subjects per group, the study had an 80% power to detect a difference between 90% and 50% of subjects who achieved profound pulpal anesthesia. Calculations were based on a chi-square test with a two-sided 5% significance level. Sample size calculations were performed using PASS 2019 (NCSS, LLC. Kaysville, UT). All calculations were derived with professional assistance.

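### Patients were told at consent that the buffer would not reduce efficacy, an assurance the documents do not support and the trial itself tests

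*Combined protocol and SAP*

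**What the plan says.** Recruitment and Enrollment of Experimental Subjects reports two statements made to every prospective participant. The first is that "the addition of a sodium bicarbonate buffer would not lead to a decrease in its efficacy". The second is that "the addition of the buffer would either have no effect or actually improve the efficacy of a standard, customary local anesthetic". The same section says that "a general script was provided to each endodontic resident outlining key points to discuss with prospective study participants", and that all 7 residents could obtain consent.

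Statistical Analysis compares the arms for "differences in the percentage of subjects who achieved profound pulpal anesthesia using chi-square tests". On the level it says "A 5% significance level was used for all tests", and for the sample size "Calculations were based on a chi-square test with a two-sided 5% significance level". The design is 20 evaluable subjects per group, with 80% power for 90% against 50%. It does not say which arm is expected to do better.

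Buffered Anesthetic Preparation says 0.18 mL of bicarbonate enters the cartridge "after the equivalent amount of anesthetic was displaced into the holding reservoir". Verification of Buffering Capacity describes the buffer as added to a 1.8 mL cartridge and does not mention displacement. Primary Materials gives 108 mg for three cartridges without separating the arms.

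**The concern.** The second statement lists the possible results and leaves out one of them, that the buffered mixture works less well. This is a claim about the primary comparison, given to patients as settled before the comparison was made. Because it is reported beside a common script, it reads as a standard message and not as one resident's phrasing.

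Two things are at stake. The first is consent. A failed block here can mean a pain score of 4 or more during pulp access or pulpotomy, so a patient would want to know whether the experimental mixture might work less well. The second is measurement. Numbness is attested by the patient, the pulp-test reading depends on the patient signalling sensation, and the FACES score is a self-rating. A promise of equal or better effect is an expectation cue given before all three.

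**Working it through.** **1. Does the design allow for a worse result with buffer?** Inputs from Statistical Analysis: n = 20 per group, p1 = 0.90, p2 = 0.50, two-sided 5%. The mean rate is 0.70.

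- Power = Φ{[|p1 − p2|·√n − 1.96·√(2·0.70·0.30)] / √(p1q1 + p2q2)}
- = Φ{[0.4 × 4.472 − 1.96 × 0.648] / √(0.09 + 0.25)} = Φ{(1.789 − 1.270) / 0.583} = Φ(0.89) = 81.3%
- The same formula solved for 80% power gives 20 per group, as in the plan.
- A one-sided 5% test would give 89.2% power at 20 per group and would need only 16 per group.

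The plan's figure therefore reproduces as two-sided. By exact enumeration of the Pearson chi-square at 50% in both arms, the test rejects in 2.1% of trials in each direction. The analysis leaves open the direction that the consent statement rules out.

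**2. Is there evidence in the documents that a decrease is excluded?** The only verification reported is of pH: 4.35 to 7.34 under Verification of Buffering Capacity, and 4.99 to 7.14 under Quality Assurance. This shows that the buffer raises pH. It says nothing about success rates.

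**3. How do the two cartridges differ in content?** Inputs: 1.8 mL of 2% lidocaine (20 mg/mL), with 0.18 mL displaced.

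- Unbuffered: 1.80 × 20 = 36 mg per cartridge; × 3 = 108 mg.
- Buffered, with displacement: (1.80 − 0.18) × 20 = 32.4 mg per cartridge; × 3 = 97.2 mg. The difference is 10.8 mg, or 10%, and the concentration is 1.8%.
- Buffered, if buffer is only added: 36 mg in 1.98 mL = 18.2 mg/mL (1.82%). The milligrams are unchanged if all of it is injected, at a lower concentration.

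Both descriptions lower the concentration. Only the first lowers the amount of drug.

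**4. Could the trial support the assurance afterwards?** The success rates here are assumed, because the documents give no common rate. The 95% half-width for the difference is 1.96·√(2p(1 − p)/20):

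| Assumed common rate | Half-width |
|---|---|
| 50% | 31 points |
| 70% | 28 points |
| 90% | 19 points |

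If buffering lowered success from an assumed 50% to 40% or 30%, exact enumeration gives a significant finding of harm in about 8% or 24% of trials. For scale, non-inferiority with an assumed 10-point margin (one-sided 2.5%, 80% power) needs n = (1.96 + 0.842)²·2p(1 − p)/0.10² per arm. That is 142 at a 90% rate and 393 at 50%. A non-significant result at 20 per group would not establish that there is no decrease.

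**The case against.** A fair defence has five parts.

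- **Dilution does not contradict the assurance.** A reader might infer that the plan's own mixture disproves what patients were told. The documents do not support that. No section says that replacing 10% of the volume lowers efficacy, the ratio is described as the manufacturer's usual suggestion, and the higher pH may offset the lower content. The 97.2 mg figure also depends on the displacement wording. This stands: the dilution only means that a decrease cannot be assumed away.
- **Two-sided testing is a convention.** It does not show that the investigators expected harm, and the two-sided level is stated only for the sample size. This stands, but a chi-square test is non-directional in any case, and telling patients that one direction is excluded still goes beyond the evidence shown.
- **The script and the written consent are not reproduced.** Either may qualify the message, and cited work outside this text may bear on efficacy. This stands as a limit. What can be judged is the plan's own report of what participants were told.
- **No bias or loss of power follows.** A reader might infer that raised expectations shrink the difference between arms. Both arms heard the same message before blinded administration, and no section quantifies an effect. Any power figure depends on the shift assumed: exact power of 83.8% becomes 80.8% if 5% of failures in both arms turn into successes, and 77.5% if 10% do. The outcomes also have some structure, with explorer stimulation compared with the other side and two consecutive maximum pulp-test readings. This stands.
- **Patients were protected.** Discomfort paused the procedure and failures received further anesthetic. This limits the harm but does not make the statement accurate.

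**Conclusion.** The assurance is unsupported. It was given to every prospective participant, with up to 60 to be randomized, and it states as known what the trial sets out to test. The documents verify pH only. As the preparation section describes it, the buffered cartridge holds 10% less lidocaine, which makes a decrease possible but does not show one. At 20 per group the trial could not confirm the assurance either, with half-widths of about 19 to 31 points at assumed common rates of 90% to 50%.

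This is a fault of consent wording and equipoise, with an expectation cue ahead of self-reported outcomes. It is not a statistical error. The sample size, alpha and stated 80% power are unaffected, and no between-arm bias is shown provided blinding held. The conclusion assumes that the plan's account of what participants were told is accurate, and that no unseen script or consent text qualified it.

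**What to change.** - Replace both statements in the resident script, and in any matching consent text, with neutral wording: it is not known whether the buffered mixture works better, the same or less well than the standard, and the study tests this. Re-brief all 7 residents.
- Tell participants that buffer replaces part of the anesthetic in the buffered cartridge.
- Reconcile Primary Materials, Verification of Buffering Capacity and Buffered Anesthetic Preparation, so that the anesthetic content of a buffered cartridge is stated once and consistently.
- The document is written largely in the past tense. If consent is already complete, report the wording as a limitation in the trial report.

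The cost is a wording amendment and a short briefing, with possibly a few more refusals. No trial procedure, analysis or sample size changes.

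### The sections conflict on who receives the infiltrations that set the first EPT; a baseline EPT of 80 is not excluded; and the time endpoint is not pulpal onset alone

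*Combined protocol and SAP*

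**What the plan says.** **Infiltrations.** Anesthetic Administration assigns the third cartridge, as buccal and lingual infiltrations, to patients who lack soft-tissue signs in the 10 minutes after the inferior alveolar nerve blocks (IANBs). Anesthetic Testing and Documentation gives it once the patient attests to soft-tissue anesthesia. Study Procedures step 8a agrees with that, and step 8b treats patients with no signs at 10 minutes as missed blocks and withdraws them.

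**EPT criterion.** Eligibility rests on cold: "an exaggerated response to cold that lingers longer than 10 seconds" under Inclusion Criteria and "No subjects will have a negative response to cold in the proposed treatment tooth" under Exclusion Criteria. Neither section limits the baseline EPT. Under Diagnosis, the baseline test ends when the patient feels it or "if the measurements reached a maximum value of 80". After injection, pulpal anesthesia is an EPT of 80 with a second 80 to confirm (Anesthetic Testing and Documentation; step 9a). A later rule classes as failures "Patients who indicated moderate or severe pain (VAS scores of 4 or higher) elicited from the tooth undergoing treatment" at access or pulpotomy.

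**Clock.** Timing begins when "the student researcher started the timer after administering both IANBs". Staff then "waited 2 minutes after all 3 cartridges of local anesthesia had been administered and then obtained an updated EPT reading", and repeat it every 2 minutes up to 20 minutes after the IANBs. Statistical Analysis compares the time to profound pulpal anesthesia by Kaplan-Meier curves and log-rank tests.

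**The concern.** The infiltration conflict looks like a clinical drafting matter, but it reaches the endpoint. The first EPT is timed from the third cartridge, so the rule on who gets that cartridge, and when, fixes the earliest time an event can be recorded. It also decides whether patients with no signs at 10 minutes stay in the study.

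A tooth that reads 80 before injection meets the EPT criterion at its first test whatever the anesthetic does. It tells us nothing about EPT success or onset, and could dilute the planned 90% versus 50% contrast.

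If buffering brings on lip numbness earlier, it also brings testing forward. A log-rank difference could then be read as faster pulpal onset when some or all of it is earlier testing.

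**Working it through.** **1. The infiltration rule, side by side**

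| Place | Soft-tissue anesthesia by 10 min | No signs by 10 min |
|---|---|---|
| Anesthetic Administration | no infiltration stated | infiltrations |
| Anesthetic Testing and Documentation | infiltrations | missed block; grounds for withdrawal |
| Steps 8a and 8b | infiltrations | missed block; withdrawn |

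The first row cannot hold together with the other two. Under it, a patient who is numb promptly has no third cartridge, so the trigger for the first EPT is undefined.

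**2. Baseline EPT of 80**

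Inputs from Statistical Analysis: 20 per group, 90% versus 50%, chi-square, two-sided 5%, stated power 80%. The plan's figure reproduces. With pooled variance (mean rate 0.70), power = Φ{[0.40√20 − 1.96√(2 × 0.70 × 0.30)] / √(0.90 × 0.10 + 0.50 × 0.50)} = 81.3%. Exact enumeration of the uncorrected chi-square gives 83.8%, the reference below.

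Let q be the share of teeth at 80 at baseline, and v the share of those that fail on VAS. Assume that 90% and 50% describe teeth below 80, and that baseline-80 teeth fail only on VAS. Then

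rate in an arm = q(1 − v) + (1 − q) × planned rate.

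Example, q = 0.10 and v = 0.5 in both arms: 0.05 + 0.90 × 0.90 = 86%, and 0.05 + 0.90 × 0.50 = 50%.

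The documents give neither q nor v. Assumed q of 5% and 10% correspond to 0.05 × 40 = 2 and 0.10 × 40 = 4 teeth.

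| VAS failure, buffered / unbuffered | Rates, q = 5% | Exact power | Rates, q = 10% | Exact power |
|---|---|---|---|---|
| 0 / 0 | 90.5% v 52.5% | 80.8% | 91% v 55% | 77.5% |
| 50% / 50% | 88% v 50% | 78.4% | 86% v 50% | 72.5% |
| 10% / 30% | 90% v 51% | 82.1% | 90% v 52% | 80.3% |
| 10% / 50% | 90% v 50% | 83.8% | 90% v 50% | 83.8% |

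The 0 / 0 row also applies if EPT alone decides success. Excluding such teeth after the fact, one or two per arm, leaves 19 or 18 per arm and exact power of 81.5% or 78.5%.

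**3. What the time endpoint contains**

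The infiltrations total 1.8 mL at 1.8 mL per minute, about 1 minute, followed by a 2-minute wait. On the sequence in Anesthetic Testing and Documentation and step 8a:

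first EPT = soft-tissue onset + 1 + 2 minutes; earliest confirmation = first EPT + 1 minute.

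| Soft-tissue onset (min) | First EPT (min) | Earliest confirmation (min) |
|---|---|---|
| 2 | 5 | 6 |
| 5 | 8 | 9 |
| 10 | 13 | 14 |

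A first reading of 80 shows only that onset was at or before that test.

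To gauge the effect, the log-rank was simulated with 20 per arm, identical pulpal onset in both arms, and lip numbness 2 minutes earlier in one arm. Every onset time and shape here is assumed.

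- Gamma onset times, median lip onset 3 v 5 minutes, 15% never anesthetised: about 12% rejection at a median pulpal onset of 5 minutes and 7% at 7.5. Dropping only the 15% assumption raises the first figure to about 27%.
- Lognormal pulpal onset (log-SD 0.5), mean lip onset 4 v 6 minutes: 47%, 9% and 4% at medians of 5, 8 and 12 minutes.

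The nominal rate is 5%. The spread across plausible shapes is too wide to support any single figure.

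**The case against.** **No evidence of baseline-80 teeth.** No section reports one, and the required lingering response to cold makes them less likely. The 90% and 50% are also stated for subjects; if they already describe everyone enrolled, there is no shortfall against the plan. Both points stand, which is why the power figures are conditional. What remains is that step 2, "Standard of care dental exam with sensibility testing that established baseline EPT reading and VAS score", comes just before the eligibility review in step 3, which sets no EPT limit.

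**Baseline-80 teeth as automatic successes.** A reader might infer this. The documents do not support it: such a tooth still needs soft-tissue anesthesia and can fail on VAS. If VAS failure differs enough between arms, no power is lost.

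**The log-rank as invalid.** A reader might infer this too. It is not so. The plan defines pulpal anesthesia operationally, by two consecutive readings of 80 timed from the IANBs, and the log-rank is a fair comparison of that. A difference would be a real effect of the regimen. Soft-tissue time is already charted, and the documents give no gap in lip onset between arms. The point is what the result may be called.

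**The infiltration conflict as a slip.** Two places agree against one, so this may be right. The text still contradicts itself on who receives an injection and when testing starts, and a count of sections does not settle which rule was meant.

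**Conclusion.** The infiltration conflict is certain on the face of the text and reaches the time endpoint through the timing of the first EPT.

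The baseline-80 gap is also certain, but its size is unknown. With assumed shares of 5% or 10%, and 90%/50% taken to describe teeth below 80, exact power goes from 83.8% to 78.4–83.8% or 72.5–83.8%. This does not show the sample-size statement to be wrong: the stated 80% reproduces.

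The time endpoint is time from IANB to confirmed readiness under the whole regimen. If lip numbness comes earlier in one arm, the log-rank can differ with identical pulpal onset. The effect runs from negligible to large depending on onset times and shapes that the documents do not give. A claim that the planned test has a known inflated error rate for pulpal onset would go beyond them.

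**What to change.** 1. **Infiltrations.** Reconcile Anesthetic Administration with Anesthetic Testing and Documentation and steps 8a and 8b, stating who receives them and when. This review takes no view on which rule is right. Cost: a text correction.
2. **Baseline EPT.** If enrolment is open, require a reading below 80 on the treatment tooth at step 3, using the step 2 value. If it has closed, as the past tense of the conduct text suggests, report baseline-80 teeth by arm from the charted initial readings and repeat the analyses without them as a sensitivity analysis. The reading precedes allocation, so the exclusion does not depend on arm. Cost: such teeth are lost, or replaced within the 60 who may be randomized; replacement to 20 per arm keeps 83.8%. Exclusion after the fact gives 81.5% or 78.5%, lower than keeping the teeth in four of the eight scenarios above, so it serves interpretation and not power.
3. **Time endpoint.** Keep the log-rank. Label it time from IANB to confirmed readiness, meaning two consecutive readings of 80 as in step 9a. Report soft-tissue onset and the share at 80 on the first test by arm, and do not claim faster pulpal onset from the log-rank alone. Cost: a label and two descriptive rows, with no added tests or visits.

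An interval-censored onset model is not recommended. Test times depend on lip onset and may be informative. With lip and pulpal onset correlated at an assumed 0.8 and identical pulpal onset in both arms, a log-logistic version rejected about 13% and 10% of the time at median onsets of 5 and 7.5 minutes, no better than the log-rank at 11.5% and 7.5%.
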